1.3 Hypotheses

1.3.1 Primary hypotheses of retrospective study

1. H_0 : Speech understanding in quiet and in noise at the 6 months post-operative visit are equal with speech understanding in quiet and noise at the pre-operative evaluation visit
 H_1 : Speech understanding in quiet and in noise at the 6 months post-operative visit is better than speech understanding in quiet and noise at the pre-operative evaluation visit
2. H_0 : The proportion of the recipient's cohort examined showing post-operative improvement per test and listening condition is below 80% for the 6 months post-operative visit.
 H_1 : The proportion of the recipient's cohort examined showing post-operative improvement per test and listening condition is $\geq 80\%$ (Dowell, Hollow & Winton, 2004) for the 6 months post-operative visit.

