2 STATISTICS

A total of $n=150$ patients will be assessed. It is expected to enrol approximately 30 subjects per site to compensate the variability of speech understanding tests in noise across sites with a decent power per site.

At different points during follow-up data exports and interim analyses will be conducted. The first data export with available datasets is expected to take place in August 2016. Over the study period it is expected to gradually increase the number of available datasets and therefore also the number of datasets for following interim analyses. The final analysis is expected to cover 150 datasets by the end of July _____

The interim analysis will be of descriptive nature only to maintain the nominal type I error of 5%. Formal hypothesis testing will be confined to the final analysis.

The level of significance for all statistical tests is $\alpha=5\%$, 2-sided.

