2.1 Sample size calculation

For the 1st primary hypothesis about speech understanding a power calculation was carried out to estimate the ability to detect a difference amounting to 20% for a clinically relevant benefit with the Freiburger monosyllabics test between the pre-op evaluations and 6 months evaluation covering test-/retest-variability and the respective deviation. For speech understanding in noise the clinically relevant difference between pre-op evaluation and 6 months visit is expected to be 1,4 dB SNR-SRT for OLSA, 30% for HSM.

A sample of $n=150$ patients is deemed sufficient to detect meaningful differences based on dB threshold values and % correct values. The standard deviation of the difference is based upon an earlier OLSA study (CAG5149 MP3000 Optimization Trial) and assumed as 3.0 to be on the conservative side.

Table 1: Numeric Results for Paired T-Test

Null Hypothesis: Mean of Paired Differences = 0, Alternative Hypothesis: Mean of Paired

Differences ≠ 0

Power	N	Alpha	Beta	Mean of Paired Differences	S	Effect Size
0.91002	100	0.05000	0.08998	1.0	3.0	0.333
0.95888	125	0.05000	0.04112	1.0	3.0	0.333
0.98196	150	0.05000	0.01804	1.0	3.0	0.333

Source for the study parameters:

ACE OLSA Data taken from MP3000 trial:

n=58, stdev.=3.3, rho=0.76, => stddev_diff = 2.29

$$\sigma_d = \sqrt{\sigma_1^2 + \sigma_2^2 - 2\rho\sigma_1\sigma_2}$$

To test for an improvement of 20% (0.2) in speech understanding, as compared to baseline, a reference proportion of 50% (0.5) and a correlation within patient of rho=0.5 is assumed. Based upon a sample of n=150 patients, the power to detect such a difference amounts to 99.9%, c.f Table 2.

Table 2: Power estimation using McNemar exact test for paired proportions

The POWER Procedure, McNemar Exact Conditional Test

Fixed Scenario Elements	
Distribution	Exact conditional
Method	Exact
Proportion 1	0.5
Proportion 2	0.7
Correlation	0.5
Number of Sides	2
Null Ratio of Discordant Proportions	1
Nominal Alpha	0.05

Computed Power			
Index	N Pairs	Actual Alpha	Power
1	100	0.0300	0.981
2	125	0.0322	0.995
3	150	0.0348	0.999

For the 2nd primary hypothesis claiming that the proportion of patients showing post-operative improvement is ≥80%, this translates into a one-sample test with a null hypothesis reference level of 80% (i.e. 0.8).

Table 3: Numeric Results for testing $H_0: P = P_0$ versus $H_1: P \neq P_0$, 2-sided: Exact Test

Power	N	Proportion	Proportion	Difference (P1 - P0)	TargetActual		Reject H0 If	

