8.2 Statistical methods

Hypothesis testing

Formal testing of the 1st primary hypothesis claiming a difference of 20% or more for speech understanding will be carried out by using a paired t-test on differences of speech understanding (i.e. values at visit 6 months - values at pre-op) with a reference proportion of 20%. Number of patients with values greater or less than 20% will be reported.

Formal testing of the 2nd primary hypothesis claiming an improvement of 80% or more of patients showing post-operative improvement will be carried out by using a binomial test (one-sample) of improvement rates with a reference proportion of 80%.

These tests will be carried out at the final analysis only. For interim analyses, descriptive rates along with 95% confidence levels will be produced reporting the frequencies of responses along with the 95% CI based on exact methods (Clopper-Pearson) for visits pre-op, month 3 and month 6.

At the final analysis, in addition refined analyses will be carried out based on a modeling approach. This enables a more sensitive analysis allowing for covariates (such as baseline characteristics). Regression analyses will be carried out for this purpose incorporating the paired structure of observations. To this end the SAS proc genmod will be used (procedure glimmix will be used as a sensitivity analysis as it estimates random effects using a different approach). Furthermore, this modelling approach allows for:

- estimating consolidated treatment effects comparing post-baseline vs. pre-op performance.
- considering center specific deviations from the thresholds used by keeping these threshold as covariate for the binomial response (success rate).

Analyses will be carried out both based upon the ITT population and the PP set. Due to the nature of the data, i.e., paired data analyses based upon ITT, this will be considered as secondary and carried out in the perspective of a sensitivity analysis. For this purpose a random effects model is required to be used treating the patient as random effect.*.

* Brown, H. & Prescott, R. (1999). *Applied Mixed Models in Medicine*, New York: John Wiley & Sons.

Analyses based on continuous outcomes such as audiometric thresholds or electrode impedances will be carried out in a similar manner using the SAS proc mixed to account for random effects of normally distributed data.

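### SAP 8.2 tests hypothesis 1 against 20% where SAP 1.3.1 and Table 1 use zero change, and no rule says which of the several primary tests are confirmatory or which must succeed

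*SAP*

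**What the plan says.** **The null of hypothesis 1.** SAP 1.3.1 sets equality of the two visits against the alternative that "Speech understanding in quiet and in noise at the 6 months post-operative visit is better than speech understanding in quiet and noise" before surgery. Table 1 in SAP 2.1 matches this: "Null Hypothesis: Mean of Paired Differences = 0". SAP 8.2 instead restates hypothesis 1 as a gain of at least 20% and runs the paired t-test "with a reference proportion of 20" per cent. In SAP 2.1, 20% is tied to the Freiburger monosyllables; for noise, "the clinically relevant difference between pre-op evaluation and 6 months visit is expected to be 1,4 dB SNR-SRT for OLSA, 30% for HSM".

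**The error rate.** SAP 2 sets one rule: "The level of significance for all statistical tests is" 5%, two-sided. Its one safeguard concerns timing: "The interim analysis will be of descriptive nature only to maintain the nominal type I error of 5" per cent, with formal tests kept for the final analysis.

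**The number of tests.** SAP 1.3.1 has two primary hypotheses. The null of the second is that the proportion of the "cohort examined showing post-operative improvement per test and listening condition is below 80" per cent. SAP 3 applies the paired t-test to both percentage scores and dB thresholds. Protocol 9 says that the noise test depends on the clinic and that OLSA and HSM results cannot be converted linearly into one another. SAP 8.2 names one type of test per hypothesis but not the speech tests it applies to. SAP 3 calls the 80% test the secondary hypothesis; SAP 1.3.1, 2.1 and 8.2 treat it as primary.

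**The concern.** Hypothesis 1 cannot be tested as written. A patient group that gains 10 points on Freiburger improves relative to zero but falls short of 20, so the two nulls can give opposite conclusions from the same data. For OLSA the 20% reference cannot be applied at all. SAP 8.2 takes the 6-month value minus the pre-op value, so benefit is a positive difference for a percentage score but a negative one for a threshold; the direction also needs stating.

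The second matter is that nothing controls error across the final primary tests. Under a flat 5% rule, significance on any one speech test could be reported as a confirmed primary result. The study is meant to supply benchmark data, and readers would not know which results were confirmatory.

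**Working it through.** 1. **The plan's own figures reproduce.**
   - Table 1, n=150: noncentral t with 149 df and noncentrality (1.0/3.0) × √150 = 4.08 gives power 0.98196, as stated.
   - Table 2, n=150: exact McNemar gives 0.999 with actual alpha 0.0348, as stated.
   - Table 3, n=150: rejecting at ≤109 or ≥130 gives alpha 0.0187 + 0.0224 = 0.0411 and power 0.9279 at a true rate of 90%, as stated.

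2. **What the 20% reference does.** Tables 1 and 2 both give power against no change. Table 2's 99.9% is for a shift from 50% to 70%. If the null is itself a gain of 20 points and the true mean gain is 20 points, the t-test rejects in favour of benefit with probability 5%/2 = 2.5%. Neither table gives power for the test in SAP 8.2.

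3. **False claims of benefit, hypothesis 1 at zero change.** A two-sided 5% test carries 2.5% in the favourable direction.
   - Two independent tests: 1 − 0.975² = 4.9%. Under any dependence the total cannot exceed 2 × 2.5% = 5.0%.
   - Three independent tests: 1 − 0.975³ = 7.3%.
   - Three correlated tests. Assume that all 150 patients have Freiburger and each has one noise test, split 60/90, which is possible with five centres (Protocol 8.1) if each uses one noise test: "It is expected to enrol approximately 30 subjects per site". The correlation between the Freiburger and noise statistics is ρ√(n_noise/150), and it is zero between OLSA and HSM. The trivariate normal gives 6.9% at ρ=0.5 and 6.6% at ρ=0.7. A 30/120 split gives the same to 0.1 point. The split and ρ are assumptions.

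4. **False claims of benefit, three 80% tests.** Exact upper tails at p=0.8 are 0.0224 (n=150, ≥130), 0.0190 (n=90, ≥80) and 0.0121 (n=60, ≥55). Then 1 − 0.9776 × 0.9810 × 0.9879 = 5.3% under independence.

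5. **Both hypotheses on one speech test.** Under the 20% reference, a normal mean gain of 20 with SD 20/0.8416 = 23.8 (assumed) puts both nulls at their boundary. With n=150 and 400,000 simulated studies, at least one false claim of benefit occurs in 3.9%, because the two statistics correlate at 0.70.

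**The case against.** The best defence is that the family is small. Hypothesis 1 speaks of quiet and noise together; if both must improve, no adjustment is needed within it. SAP 8.2 names one formal test per hypothesis, Table 3 powers a single binomial test at n=150, and SAP 5 defines response without reference to a scale, so a pooled response is conceivable. That leaves two tests and at most 5.0%. SAP 2.1 also plans for real gains, in which case the zero-change nulls are false and only the 80% tests carry risk, at 5.3%. Finally, this is a retrospective benchmark collection whose means, rates and 95% CIs stay usable.

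Much of this stands: it makes the inflation conditional and modest. It does not supply the missing rule. No analysis section says that quiet and noise must both succeed; SAP 3 runs separate tests for percentages and dB; hypothesis 2 is worded test by test; and the SAP plans formal tests of named primary hypotheses. None of it touches the conflict over the null.

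A reader might infer larger figures:
- **14.3%** (1 − 0.95³) counts rejections towards worsening, which cannot be reported as benefit.
- **26.5%, or 14.1% favourable,** for six independent tests needs both nulls at their boundary on every speech test. With zero mean change and symmetric differences, no more than about half the patients improve, so a false 80% claim on that test is practically excluded.

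**Conclusion.** The conflict over the null is an error in the text, whatever reading is taken of the rest: SAP 8.2 contradicts SAP 1.3.1 and Table 1, and its reference cannot apply to OLSA.

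The multiplicity gap is real but conditional. If any one success counts, false claims of benefit reach 7.3% for hypothesis 1 over three independent tests (6.6% to 6.9% correlated) and 5.3% for hypothesis 2, against 2.5% for one test. With two tests the total stays at or below 5.0%. The count of three, the 60/90 split, ρ and independence are assumptions, because the SAP lists none of them.

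Three stronger inferences are not supported. The plan does not ignore type I error: keeping interim analyses descriptive is sound. Inflation is not demonstrated, since an all-must-succeed reading of hypothesis 1 is open. And the secondary label in SAP 3 does not create a hierarchy, since three other sections treat the 80% test as primary and no gatekeeping is attached to the label.

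**What to change.** **Null.** In SAP 8.2, test hypothesis 1 against zero change for each speech test, state the direction of benefit, and report descriptively how many patients exceed that test's own relevant difference. If the 20% reference is kept, limit it to Freiburger and restate hypothesis 1 and its power.

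**Confirmatory tests.** In SAP 2 and 8.2, list them (pre-op daily listening versus 6-month best aided). Then either state that hypothesis 1 requires success in quiet and in noise, or fix one order at full two-sided 5%, stopping at the first test not significant in favour of benefit:
1. Hypothesis 1 for Freiburger, then for the noise test with more patients, then for the other.
2. Hypothesis 2 in the same order.

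Under the first option, hypothesis 2 still needs its order. Set the order from counts of available tests before the final export, not from interim results. Report all other tests as estimates with 95% CIs. Say how the wording on test and listening condition in hypothesis 2 is read. In SAP 3, relabel the 80% test as the second primary hypothesis.

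**Cost.** A few sentences and no extra patients. Later tests lose confirmatory status if an earlier one fails:
- Once hypothesis 1 has succeeded on all three, with a true rate of 90%, independence and a 60/90 split, hypothesis 2 is confirmed with probability 92.8% for Freiburger, 0.9279 × 0.7125 = 66.1% for the larger noise test, and 0.6611 × 0.4372 = 28.9% for the smaller. The 92.8% also needs paired Freiburger data on all 150 patients.
- Hypothesis 1 may itself stop the sequence. If OLSA has n=60 and SD 3.0, its power is 94.5% at 1.4 dB and 71.9% at 1.0 dB. If the other hypothesis 1 tests pass, Freiburger's 80% test is then confirmed with probability 0.9447 × 0.9279 = 87.7% or 0.719 × 0.9279 = 66.7%.
- An equal split over six tests avoids this dependence, but it lowers Freiburger's 80% test to 75.8% and that OLSA test at 1.0 dB to 44.7%.

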2.1 Sample size calculation

For the 1st primary hypothesis about speech understanding a power calculation was carried out to estimate the ability to detect a difference amounting to 20% for a clinically relevant benefit with the Freiburger monosyllabics test between the pre-op evaluations and 6 months evaluation covering test-/retest-variability and the respective deviation. For speech understanding in noise the clinically relevant difference between pre-op evaluation and 6 months visit is expected to be 1,4 dB SNR-SRT for OLSA, 30% for HSM.

A sample of $n=150$ patients is deemed sufficient to detect meaningful differences based on dB threshold values and % correct values. The standard deviation of the difference is based upon an earlier OLSA study (CAG5149 MP3000 Optimization Trial) and assumed as 3.0 to be on the conservative side.

Table 1: Numeric Results for Paired T-Test

Null Hypothesis: Mean of Paired Differences = 0, Alternative Hypothesis: Mean of Paired

Differences ≠ 0

Power	N	Alpha	Beta	Mean of Paired Differences	S	Effect Size
0.91002	100	0.05000	0.08998	1.0	3.0	0.333
0.95888	125	0.05000	0.04112	1.0	3.0	0.333
0.98196	150	0.05000	0.01804	1.0	3.0	0.333

Source for the study parameters:

ACE OLSA Data taken from MP3000 trial:

n=58, stdev.=3.3, rho=0.76, => stddev_diff = 2.29

$$\sigma_d = \sqrt{\sigma_1^2 + \sigma_2^2 - 2\rho\sigma_1\sigma_2}$$

To test for an improvement of 20% (0.2) in speech understanding, as compared to baseline, a reference proportion of 50% (0.5) and a correlation within patient of rho=0.5 is assumed. Based upon a sample of n=150 patients, the power to detect such a difference amounts to 99.9%, c.f Table 2.

Table 2: Power estimation using McNemar exact test for paired proportions

The POWER Procedure, McNemar Exact Conditional Test

Fixed Scenario Elements	
Distribution	Exact conditional
Method	Exact
Proportion 1	0.5
Proportion 2	0.7
Correlation	0.5
Number of Sides	2
Null Ratio of Discordant Proportions	1
Nominal Alpha	0.05

Computed Power			
Index	N Pairs	Actual Alpha	Power
1	100	0.0300	0.981
2	125	0.0322	0.995
3	150	0.0348	0.999

For the 2nd primary hypothesis claiming that the proportion of patients showing post-operative improvement is ≥80%, this translates into a one-sample test with a null hypothesis reference level of 80% (i.e. 0.8).

Table 3: Numeric Results for testing $H_0: P = P_0$ versus $H_1: P \neq P_0$, 2-sided: Exact Test

Power	N	Proportion	Proportion	Difference (P1 - P0)	TargetActual		Reject H0 If	
		Given H0 (P0)	Given H1 (P1)		Alpha	Alpha	Beta	<=R >=R
0.3947	100	0.8000	0.8750	0.0750	0.0500	0.0326	0.6053	71 89
0.6058	125	0.8000	0.8750	0.0750	0.0500	0.0440	0.3942	90 109
0.6761	150	0.8000	0.8750	0.0750	0.0500	0.0411	0.3239	109 130
0.7030	100	0.8000	0.9000	0.1000	0.0500	0.0326	0.2970	71 89
0.8811	125	0.8000	0.9000	0.1000	0.0500	0.0440	0.1189	90 109
0.9279	150	0.8000	0.9000	0.1000	0.0500	0.0411	0.0721	109 130
0.9287	100	0.8000	0.9250	0.1250	0.0500	0.0326	0.0713	71 89
0.9876	125	0.8000	0.9250	0.1250	0.0500	0.0440	0.0124	90 109
0.9958	150	0.8000	0.9250	0.1250	0.0500	0.0411	0.0042	109 130

Assuming a difference of 10% (i.e. 0.1) with respect to H_0 stating an improvement rate of 0.8, a sample of $n=150$ patients yields a power of 92.8% (Other scenarios are shown for completeness, c.f Table 3).

Power calculations were carried out with software PASS 11: Hintze, J. (2011). PASS 11. NCSS, LLC. Kaysville, Utah, USA and with SAS software proc power, Vs. 9.4.

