3 CONDUCT OF STATISTICAL ANALYSIS

The statistical analyses including reformatting datasets and derivation of outcomes data-management will be carried out by numerics data gmbh, [REDACTED] (i.e. subcontractor).

The speech understanding data will be collected as % correct for either in-quiet or in-noise environments, or speech reception threshold in dB SNR for an in-noise environment.

Electrode location due to proximity to the modiolus, along with duration of deafness and age at onset of hearing loss, will be used as potential variables for the speech understanding. Therefore different categories will be implemented separating patients with a duration of ≤ 30 and > 30 years of age; onset of hearing loss at ≥ 5 and < 5 years of age, close proximity to the modiolus and distanced from the modiolus at the basal turn.

The primary hypothesis will be tested using a one sample (paired) t-test with the difference of the 6 month values versus the baseline values as outcome. This will be done for % speech understanding and dB threshold values. Results will be reported with mean and a 95% CI. The analysis will also be complemented by an analysis of covariance approach, that is, the pre-treatment values are treated as covariate while the values at month 6 are treated as outcome variable. This allows for a sensitive approach to account for baseline covariates such as age, gender and clinic, enabling meaningful average

estimates for specific subgroups with the aim to explore whether the treatment effects hold for the whole study population or are restricted to specific subgroups only. Least squares mean differences are calculated for this purpose.

The secondary hypothesis will be examined using a binomial exact test with a $p=0.8$ as H_0 reference level. This rather crude test will be complemented by regression analyses as described in section 8.2.

The analyses will be carried out with the SAS software (SAS Version 9.4, SAS Institute, Cary, NC, U.S.A.).

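### The 99.9% power for the first primary hypothesis belongs to a McNemar test that is never performed; for the planned paired t-test it holds only against a null of zero, not against the 20% reference in SAP section 8.2

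*SAP*

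**What the plan says.** SAP section 2.1 sets out the power for the first primary hypothesis and names a 20% difference on the Freiburg monosyllable test as the clinically relevant benefit. It then gives two calculations.

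- Table 1 is a paired t-test against zero, with a mean difference of 1.0 and an SD of 3.0. The SD comes from an earlier OLSA study, so it is a dB figure. Power at n=150 is 0.98196.
- Table 2 is introduced with "To test for an improvement of 20% (0.2) in speech understanding", and "a reference proportion of 50% (0.5) and a correlation within patient of rho=0.5 is assumed". Its title is "Table 2: Power estimation using McNemar exact test for paired proportions". The null is a discordant ratio of 1, meaning no difference. The text concludes: "Based upon a sample of n=150 patients", "the power to detect such a difference amounts to 99.9" per cent.

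The planned analysis is different. SAP section 3 says "The primary hypothesis will be tested using a one sample (paired) t-test" on the month-6 minus baseline difference, for both % correct and dB values. SAP section 8.2 says the first hypothesis is tested "by using a paired t-test on differences of speech understanding", and adds a reference value of 20%. Section 1.3 of the SAP and section 7.3 of the protocol both state the null as equality of pre-operative and 6-month speech understanding. SAP section 5 derives one binary variable per patient: better, or else worse or equal, relative to pre-op. The second primary hypothesis has its own one-sample binomial test.

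**The concern.** Table 2 takes a mean score that rises from 50% to 70% and treats it as the share of patients with a yes/no outcome that rises from 50% to 70%. These are different quantities. McNemar's test needs a yes/no value before surgery and another after it for each patient. The only binary variable that section 5 derives is already a change, so there are no data for that test, and the SAP does not name it outside the power section.

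The power of the planned t-test depends on two things that Table 2 does not supply: the SD of the paired % correct difference, and the null value. No SD on the % correct scale appears anywhere. The null value is given two ways: zero in the stated hypotheses and 20% in section 8.2. Under the second, the gain that section 2.1 sets out to detect is itself the null value.

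At stake is the headline power claim for a primary hypothesis. A reader who puts section 2.1 beside section 8.2 would expect near-certain success in a scenario where the test as written will almost always fail to show benefit.

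**Working it through.** **Inputs from the SAP:** n=150; two-sided alpha 0.05 (section 2); proportions 0.5 and 0.7, rho 0.5 (section 2.1); planned gain 20 points (section 2.1); reference 20% (section 8.2) or equality (section 1.3). **Assumed, because the SAP gives none:** SD of the % correct difference, shown over a range. All figures assume 150 complete pairs on one test.

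**1. Reproduce Table 2.** The proportion positive on both occasions is p11 = p1·p2 + rho·√(p1·q1·p2·q2) = 0.35 + 0.5·√(0.25 × 0.21) = 0.4646. The discordant cells are 0.5 − 0.4646 = 0.0354 and 0.7 − 0.4646 = 0.2354. Averaging the two-sided exact binomial test over the number of discordant pairs gives:

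| N | Power, recomputed | Power, SAP | Actual alpha, recomputed | Actual alpha, SAP |
|---|---|---|---|---|
| 100 | 0.9806 | 0.981 | 0.0300 | 0.0300 |
| 125 | 0.9953 | 0.995 | 0.0322 | 0.0322 |
| 150 | 0.9990 | 0.999 | 0.0348 | 0.0348 |

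Table 1 also reproduces (0.91002, 0.95888, 0.98196). The arithmetic is right. The mismatch is between the test powered and the test planned.

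**2. Paired t-test power.** The noncentrality is (true gain − null value)/SD × √n, with √150 = 12.247. The two-sided critical value on 149 df is 1.976.

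**3. Null of zero, true gain 20 points.**

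| SD of difference (points) | Power, n=150 |
|---|---|
| 10 to 40 | above 99.9% |
| 48 | 99.9% |
| 50 | 99.8% |
| 60 | 98.2% |

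The SD at which power is exactly 99.9% is 48.2 points.

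**4. Why Table 2 lands on the same figure.** Put its inputs into the SAP's own formula for the SD of a difference: √(0.25 + 0.21 − 2 × 0.5 × √(0.25 × 0.21)) = √0.2309 = 0.480, or 48 points. A paired t-test against zero with that SD gives 0.9990.

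**5. Null of 20 points (section 8.2), n=150.** With a true gain of 20 the noncentrality is 0. The test rejects 5% of the time in total and 2.5% in the favourable direction, whatever the SD.

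| Assumed SD | Noncentrality, true gain 25 | Power, true gain 25 | Gain for 90% power |
|---|---|---|---|
| 20 | 5/20 × 12.247 = 3.06 | 86% | 25.3 |
| 25 | 5/25 × 12.247 = 2.45 | 68% | 26.7 |
| 30 | 5/30 × 12.247 = 2.04 | 53% | 28.0 |

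The last column uses the standardised distance that gives 90% power at n=150. A distance of 20 points reaches 90% at an SD of 75.08, so the ratio is 20/75.08 = 0.2664. The gain needed is then 20 + 0.2664 × SD.

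**The case against.** The strongest reply is that Table 2 is mislabelled but does no harm. Its inputs are equivalent to a difference SD of 48 points, and a t-test against zero with that SD has the same 99.9%. Scores bounded at 0 and 100 with means of 50 and 70 can have SDs of at most 50 and √(70 × 30) = 45.8. At correlation 0.5 the SD of the difference therefore cannot exceed 50, which still gives 99.8%. Even at correlation 0 it is at most √(50² + 45.8²) = 67.8, which gives 94.8%. In addition, Table 1 is a paired t-test, and its standardised effect of 0.333 corresponds to a 20-point gain with an SD of 60.

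Most of this stands for a null of zero. A reader might infer that the 99.9% tells us nothing about the planned test, or that the study is too small. The documents support neither reading: against equality, 150 pairs are ample over any plausible SD, and the dB outcome has its own t-test calculation. But the SAP does not make this argument. It gives no SD for scores, and nobody could recover one from a McNemar table without the steps above.

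It is also fair to say that the low figures come from the 20% reference and not from the choice of McNemar, and that any two-sided 5% test rejects 2.5% in the favourable direction when the truth equals its null. That is correct, and it means that swapping in a t-test table against zero would not by itself cure the problem. It does not rescue the stated power for the test in section 8.2, where the gain being powered is the null value.

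**Conclusion.** The point holds in this form: the 99.9% is the power of a test that the SAP does not perform, and whether the number is true of the planned t-test depends on a null that the SAP states in two ways.

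- **Null of equality (SAP 1.3, protocol 7.3):** about 99.9% or more for a 20-point gain, for any SD of the difference up to about 48 points. The number stands; its basis does not.
- **Reference of 20% (SAP 8.2):** the number is wrong. A true gain of 20 points gives a favourable rejection 2.5% of the time. A gain of 25 points gives 86%, 68% or 53% power at SDs of 20, 25 or 30.

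The results for a zero null need no precise SD. The figures for a 25-point gain and for 90% power do depend on the assumed SDs of 20 to 30, which are not in the documents. Everything rests on 150 complete pairs on one test. The protocol (section 9) says that noise tests differ by clinic, so a % correct noise test may have fewer. With 30 pairs, a 20-point gain against zero has 94.2% power at an SD of 30 and 75.4% at 40.

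**What to change.** 1. State one null for the first primary hypothesis, and make SAP section 1.3, SAP section 8.2 and protocol section 7.3 agree on it.
2. Replace Table 2 with paired t-test power for the difference in % correct, at n=150, over a stated and preferably sourced range of SDs, against that same null.
3. Restate the power sentence to match. If the null is zero, it can say that power for a 20-point gain is about 99.9% or more for SDs up to about 48 points. If the null is 20 points, it should give the gain beyond 20 that is detectable: about 5.3, 6.7 or 8.0 points for 90% power at SDs of 20, 25 or 30.

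The cost is one recalculated table, one restated sentence and one reconciled null value, with a matching protocol edit if the null changes. No patients or data are added. The downside is that the stated power becomes less favourable if the 20% reference is kept.
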